16.3.4.5.3 Incomplete dates for last known date patient alive or death

All dates must be completed with day, month and year. If the day is missing, the 15th of the month will be used for incomplete death dates or dates of last contact.

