16.3.4.5.1 Calculation of 'time to event' variables

Time to event = end date - start date + 1 (in days)

When no post-baseline tumor assessments are available, the date of randomization/start of treatment will be used as end date (duration = 1 day) when time is to be censored at last tumor assessment, i.e. time to event variables can never be negative.

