Safety summaries (tables, figures) include only data from the on-treatment period with the exception of baseline data which will also be summarized where appropriate (e.g. change from baseline summaries). In addition, a separate summary for death including on treatment and post treatment deaths will be provided. In particular, summary tables for adverse events (AEs) will summarize only on-treatment events, with a start date during the on-treatment period (*treatment-emergent* AEs). However, all safety data (including those from the post-treatment period) will be listed and those collected during the pre-treatment and post-treatment period will be flagged.

Additional summaries will be displayed to report deaths, all AEs, AEs related to study treatment, all SAEs and SAEs related to study treatment collected up to 150 days after last administration of LAG525/spartalizumab or up to 30 days after the last dose of carboplatin whichever comes last..

Last contact date

The last contact date will be derived for subjects not known to have died at the analysis cut-off using the last complete date among the following:

Table 2-1 Last contact date data sources

Source data	Conditions
Date of Randomization	No Condition
Last contact date/last date subject was known to be alive from Survival Follow-up page	Subject status is reported to be alive, lost to follow-up or unknown
Start/End dates from further antineoplastic therapy	Non-missing medication/procedure term.
Start/End dates from study treatment pages	Non-missing dose. Doses of 0 are allowed.
End of treatment date from disposition page at end of treatment	No condition.
Tumor (RECIST / iRECIST) assessment date	Result is not missing
Verification for treatment beyond RECIST1.1 PD	At least one non missing parameter value
Laboratory/PK/IG collection dates	Was sample taken? = 'Yes'.
Vital signs date	At least one non-missing parameter value
Performance Status date	Non-missing performance status
Start/End dates of AE	Non-missing verbatim term

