The last contact date is defined as the latest complete date from the above list on or before the data cut-off date. The cut-off date will not be used for last contact date, unless the subject was seen or contacted on that date. No date post cut-off date will be used. Completely imputed dates (e.g. the analysis cut-off date programmatically imputed to replace the missing end date of a dose administration record) will not be used to derive the last contact date. Partial date imputation is allowed for event (death)/censoring if coming from Survival eCRF.

The last contact date will be used for censoring of subjects in the analysis of overall survival.

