Discontinuation due to disease progression (collected on the ‘Treatment disposition’ and ‘Post treatment follow up disposition’ eCRF pages) without supporting objective evidence satisfying progression criteria per RECIST 1.1 will not be considered disease progression for PFS derivation. Clinical deterioration will not be considered as a qualifying event for progression.

Clinical benefit rate (CBR)

CBR is defined as the proportion of subjects with a best overall response (BOR) of confirmed CR or PR, or SD lasting 24 weeks or longer, according to RECIST 1.1 criteria. A subject will be considered to have SD for 24 weeks or longer if a SD response is recorded at (24-1) weeks or later from randomization, allowing for the ± 1 week visit window for tumor assessments. CBR will be calculated using the FAS based on the investigators’ tumor assessments.

Overall Survival (OS)

Overall Survival is defined as the time from date of randomization to date of death due to any cause. All deaths occurring on or before the cut-off date in the FAS will be used in the OS analysis. If a subject is not known to have died, then OS will be censored at the latest date the subject was known to be alive (on or before the cut-off date).

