5.1.2.1 Other imputations

Incomplete date of initial diagnosis of cancer and date of most recent recurrence

Missing day is defaulted to the 15th of the month and missing month and day is defaulted to 01-Jan.

Incomplete assessment dates for tumor assessment

All investigation dates (e.g. MRI scan, CT scan) must be completed with day, month and year. If one or more assessment dates are incomplete but other investigation dates are available, this/these incomplete date(s) are not considered for calculation of the assessment date and assessment date is calculated as the latest of all investigation dates (e.g. MRI scan, CT scan) if the overall response at that assessment is CR/PR/SD/UNK. Otherwise – if overall response is progression – the assessment date is calculated as the earliest date of all investigation dates at that evaluation number. If all measurement dates have no day recorded, the 1st of the month is used. If the month is not completed, for any of the investigations, the respective assessment will be considered to be at the date which is exactly between previous and following assessment. If a previous and following assessment is not available, this assessment will not be used for any calculation.

Applying the cut-off to tumor assessment

For tumor related assessments, if an evaluation has some assessments done prior to cut-off date and others after the cut-off date, then the evaluation is considered post-cut-off date and will be excluded from analysis.

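### Imputed death dates, and year-only diagnosis or recurrence dates, are not checked against known dates, so a few records can carry impossible or one-sidedly biased times

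*Protocol*

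**What the plan says.** **Death and last contact.** Protocol 16.3.4.5.3 asks for complete dates and then gives the fallback: "If the day is missing, the 15th of the month will be used for incomplete death dates or dates of last contact". SAP 2.1.1 (Last contact date) lets such dates into the survival analysis: "Partial date imputation is allowed for event (death)/censoring if coming from Survival eCRF". Neither place sets a lower limit on the imputed date.

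**Diagnosis and recurrence.** SAP 5.1.2.1, for initial cancer diagnosis and most recent recurrence: "Missing day is defaulted to the 15th of the month and missing month and day is defaulted to 01-Jan". Again there is no comparison with another date.

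**Where checks do exist.** SAP 5.1.1 compares an imputed dose end date with the treatment start and replaces it if it is earlier. SAP Table 5-2 compares a completely imputed adverse event or concomitant medication end date with that record's start. SAP Table 5-1 uses 1 July for a year-only start date in a year before treatment began.

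**The latest-date rule.** SAP 2.1.1 takes the latest of many dates, randomization included, but its scope is limited: "The last contact date will be derived for subjects not known to have died at the analysis cut-off". It governs censoring dates and puts no floor under a death date.

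**The concern.** OS and PFS both run from randomization, and death is an event in each. A death known only by month goes to the 15th even if the participant was scanned or seen later in that month. Take a progression scan on 20 March and a death recorded as March. The rule dates the death 15 March, so the PFS event becomes a death five days before the scan took place. With randomization on 20 March and death in March, OS ends before it starts.

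For cancer history, a missing day goes to mid-month, but a missing month and day go to the earliest possible date of the year. Every error therefore lengthens the time since the event. A year-only recurrence in the same year as a fully dated diagnosis falls before that diagnosis, unless the diagnosis was itself on 1 January. These dates feed the disease-history summaries in SAP 2.3.3.

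So a death date, which is an endpoint event, has less protection than the end date of a concomitant medication.

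**Working it through.** The documents state no figure that depends on these rules, so there is none to reproduce. The check is calendar arithmetic.

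**Inputs from the documents**
- Time to event = end - start + 1 days (Protocol 16.3.4.5.1).
- Month = 30.4375 days (SAP 2.1.1).
- Survival calls every 12 weeks (Protocol 9.2.3).
- 88 randomized (Protocol, Amendment 4: 20 + 34 + 34).
- Background median OS of 9-12 months (Protocol 1.1.1).

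**Assumptions**
- Day of death is uniform over the calendar.
- The gap from last contact to death is not given, so a range is shown.
- The share of incomplete dates is not given.

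**1. Error of the 15th.** Error = 15 - true day, over the 365 days of 2019: mean -0.72 days, range -16 to +14. The imputed date is too early for 185 days, too late for 168 and exact for 12.

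**2. Death dated before a documented contact.** With a gap of g days, this happens when true day - 15 > g.

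| Gap (days) | Probability, given the day is missing |
|---|---|
| 1 | 47% |
| 3 | 41% |
| 7 | 28% |
| 14 | 5% |
| 16 or more | 0% |

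Averaging over assumed gap distributions:
- Exponential with mean 14, 21 or 42 days: about 19-21%, 14-16% and 8-9%. The spread comes from rounding gaps to whole days. The mean shortfall is about 6 days.
- Uniform over the 12-week call interval: about 4-5%.

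The largest shortfall is 31 - 15 = 16 days.

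**3. Death dated before randomization.** This needs randomization after the 15th and death in the same calendar month.
- Example: randomized on the 20th gives OS = 15 - 20 + 1 = -4 days.
- Worst case: randomized on the 31st gives 15 - 31 + 1 = -15 days.
- Probability: average 1 - exp(-lambda x days left in the month) over all randomization days, counting zero for days 1-15, with lambda = ln 2 / (median OS x 30.4375).
- Result: 1.04% at a median of 9 months and 0.78% at 12 months. Even if every death date lacked its day, that is 88 x 0.0104 = 0.9 or 88 x 0.0078 = 0.7 participants.

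**4. Year-only date set to 1 January.**
- True date uniform over 365 days: mean overstatement (0 + 364)/2 = 182 days; 182/30.4375 = 5.98 months; maximum 364/30.4375 = 11.96 months.
- With 1 July instead, which is 181 days after 1 January, the mean error is 182 - 181 = 1 day (0.5 in a leap year).
- A recurrence in the randomization year must lie before randomization. With randomization on 1 July, the mean overstatement is 181/2 = 90.5 days, or 3.0 months.
- Effect on a whole-cohort mean, for an assumed share of year-only records: 5% gives 0.05 x 5.98 = 0.3 months, 10% gives 0.6 and 20% gives 1.2.

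**The case against.** **Partial dates should be rare.** Protocol 16.3.4.5.3 itself requires complete dates, Protocol 11.1 and 11.2 provide validation checks and queries, and Protocol 16.3.4 presents the rules as guidance, with programs to be adapted by study. This stands and limits how many records are affected. It does not say what happens to those that remain, and the SAP adds no bound.

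**Nothing decision-relevant moves.** This stands. The primary endpoint is ORR. OS and PFS are Kaplan-Meier descriptions by arm with no test, and baseline tables carry no inference. The relapse-free-interval subgroups depend on an arm showing preliminary efficacy, and Amendment 4 reports that none did.

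**The analysis is largely done.** The primary cut-off was 27-Feb-2020, and the amended SAP serves a close-out report on safety and PK. This mostly stands, though SAP 2.15 still names OS among the data for the final analysis.

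Four stronger readings are tempting, and the documents do not support them:
- *Imputed deaths always shorten survival.* That is true only among deaths placed before a known contact. Overall the errors nearly cancel.
- *Time since diagnosis is overstated by 6 months in this trial.* That figure belongs to year-only records, whose share is unknown.
- *Up to a fifth of day-missing deaths are misplaced.* This rests on an assumed gap of about two weeks. With gaps spread over the call interval it is about 5%.
- *The protocol contradicts its own statement that* "time to event variables can never be negative". In Protocol 16.3.4.5.1 that remark explains censoring when there is no post-baseline scan. It neither covers nor corrects an imputed death date.

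**Conclusion.** The point holds as a small programming defect. Two stated rules can produce dates that the trial's own data rule out, and the SAP already uses the missing comparison for less important dates.

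For deaths with a missing day, the error is at most 16 days and averages -0.7 days. A date before a documented contact occurs in roughly 5% to 21% of such deaths, depending on the assumed gap. A date before randomization is expected in fewer than one of 88 participants even in the extreme case. For year-only history dates, the bias runs one way, 0 to 12 months. Its mean is about 6 months if dates are uniform over the year, and about 3 for a recurrence in the year of a 1 July randomization. The documents do not give the number of records of either kind. The conclusion on ORR does not change.

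**What to change.** **Death (Protocol 16.3.4.5.3, carried into SAP 2.1.1).** Keep the 15th. If it is not after the last complete date on which the participant is known to have been alive, randomization included, use the day after that date, but no later than the month end or the data cut-off. OS then cannot be negative, and a progression scan earlier than the death stays the PFS event.

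**Diagnosis and most recent recurrence (SAP 5.1.2.1).** For year-only dates use 1 July, not after randomization and, for recurrence, not before initial diagnosis. One refinement is worth considering: where a bound cuts the year short, use the midpoint of the remaining interval. With randomization on 1 July, the bound alone would put the recurrence on the randomization date and turn a mean bias of about +3 months into about -3.

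**Cost.** Two sentences and one date comparison, using data already collected. The small downside is that a few dates may differ from those in the primary report; list those records in the close-out report.

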16.3.4.5.4 Non-target lesion response

If no non-target lesions are identified at baseline (and therefore not followed throughout the study), the non-target lesion response at each assessment will be considered 'not applicable (NA)'.

16.3.4.5.5 Study/project specific programming

The standard analysis programs need to be adapted for each study/project.

16.3.4.5.6 Censoring reason

In order to summarize the various reasons for censoring, the following categories will be calculated for each time to event variable based on the treatment completion page, the study evaluation completion page and the survival page.

For survival the following censoring reasons are possible:

- Alive
- Lost to follow-up

For PFS and TTP (and therefore duration of responses) the following censoring reasons are possible:

- Ongoing without event
- Lost to follow-up
- Withdrew consent
- Adequate assessment no longer available*
- Event documented after two or more missing tumor assessments (optional, see Table 16-6)
- Death due to reason other than underlying cancer (only used for TTP and duration of response)
- Initiation of new anti-cancer therapy
- *Adequate assessment is defined in Section 16.3.3.2.7. This reason is applicable when adequate evaluations are missing for a specified period prior to data cut-off (or prior to any other censoring reason) corresponding to the unavailability of two or more planned tumor assessments prior to the cut-off date. The following clarifications concerning this reason should also be noted:
- This may be when there has been a definite decision to stop evaluation (e.g. reason="Sponsor decision" on study evaluation completion page), when patients are not followed for progression after treatment completion or when only UNK assessments are available just prior to data cut-off).
- The reason "Adequate assessment no longer available" also prevails in situations when another censoring reason (e.g. withdrawal of consent, loss to follow-up or alternative anticancer therapy) has occurred more than the specified period following the last adequate assessment.
- This reason will also be used to censor in case of no baseline assessment.

References (available upon request) 16.3.5

Dent S, Zee (2001) application of a new multinomial phase II stopping rule using response and early progression, J Clin Oncol; 19: 785-791

Eisenhauer E, et al (2009) New response evaluation criteria in solid tumors: revised RECIST guideline (version 1.1). European Journal of Cancer, Vol.45: 228-47

Ellis S, et al (2008) Analysis of duration of response in oncology trials. Contemp Clin Trials 2008; 29: 456-465

EMA Guidance: 2012 Guideline on the evaluation of anticancer medicinal products in man

FDA Guidelines: 2005 Clinical Trial Endpoints for the Approval of Cancer Drugs and Biologics, April 2005

mL	milliliter
NCI	National Cancer Institute
NMQ	Novartis MedDRA Queries
o.d.	Once Daily
ORR	Overall Response Rate / Objective Response Rate
OS	Overall Survival
PAS	Pharmacokinetic Analysis Set
PD	Progressive Disease
PD-1	Programmed Death 1
PD-L1	Programmed Death-Ligand 1
PD-L2	Programmed Death-Ligand 2
PDI	Planned Dose Intensity
PFS	Progression-Free Survival
PgR	Progesterone receptor
PK	Pharmacokinetics
PR	Partial Response
PRO	Patient-reported Outcomes
PT	Preferred Term
qd	Qua'que di'e / once a day
RDI	Relative Dose Intensity
RAP	Report and Analysis Process
RECIST	Response Evaluation Criteria in Solid Tumors
sd	Standard deviation
SD	Stable Disease
SAE	Serious Adverse Event
SAP	Statistical Analysis Plan
SMQ	Standardized MedDRA Queries
SOC	System Organ Class
SOD	Sum Of Diamaters
TA	Tumor Assessment
TBL	Total Bilirubin
TFLs	Tables, Figures, Listings
████	████████████████████
TNBC	Triple Negative Breast Cancer
TP	Time Point
TTR	Time To Response
ULN	Upper Limit of Normal
UNK	Unknown

WHO	World Health Organization
WHO-DD	WHO-Drug Dictionary
WHO DRL	WHO Drug Reference Listing

1 Introduction

This statistical analysis plan (SAP) describes all planned analyses for the clinical study reports (CSR, either CSR for the primary analysis or CSR for the final analysis) of study CLAG525B2101, a phase II, randomized, open-label, three-arm multicenter study of LAG525 given in combination with spartalizumab (PDR001), or with spartalizumab and carboplatin, or with carboplatin, as first or second line therapy in patients with advanced triple-negative breast cancer.

The content of this SAP is based on protocol CLAG525B2101 v04. All decisions regarding final analysis, as defined in the SAP document, have been made prior to database lock of the study data. This SAP has been amended before the final close-out CSR for safety and PK analysis, for which no inferential analysis is planned.

1.1 Study design

This is a randomized, phase II, open-label, three-arm, multicenter study evaluating the safety and efficacy of LAG525 given in combination with spartalizumab, or LAG525 with spartalizumab and carboplatin, or LAG525 with carboplatin, as first or second line therapy in patients with advanced triple-negative breast cancer. Approximately 96 subjects will be randomized to one of the following treatment arms in 1:1:1 ratio:

- LAG525 + PDR001
- LAG525 + PDR001 + carboplatin
- LAG525 + carboplatin

Randomization will be stratified by the following factors:

- Presence of liver metastasis (Yes / No)
- Line of therapy (First line: following disease progression after adjuvant or neoadjuvant therapy / Second line: following one disease progression in advanced or metastatic setting)

[figure not shown]
With protocol amendment 3, enrollment to treatment Arm 1 (LAG525 + PDR001) was prematurely closed. Novartis and the study steering committee decided to prematurely stop enrollment of subjects to Arm 1 after data review showed an increased treatment discontinuation rate due to progressive disease in Arm 1 as compared to Arms 2 and 3 (both containing carboplatin)

Overall response rate (ORR), as assessed by local investigators review of tumor response and using RECIST 1.1 criteria, is the primary endpoint in this study.

The primary analysis was conducted when all subjects have been followed for efficacy (tumor assessments) for at least 24 weeks or discontinued tumor assessments for any reason prior to 24 weeks. The primary analysis data will be summarized in the primary clinical study report (CSR). Any additional data for subjects continuing to receive study treatment past the data cut-off date for the primary CSR, as allowed by the protocol, will be reported in the final CSR on completion of the study.

No formal interim analysis is planned for this trial.

Figure 1-1 Study Design

[figure not shown]
**With protocol amendment 3, enrollment to treatment Arm 1 (LAG525 + spartalizumab) was prematurely closed
 Δ Upon the release of protocol amendment #4, ongoing patients who will transfer into PTA program (roll over study or PSDS) only EOT visit will be performed but no safety, efficacy and survival follow-up
 + Patients who had stopped study treatment more than 150 days will be discontinued from the study – see Section 9.1.1 for details. Survival follow-up period is removed after protocol amendment #4 is approved
 † with implementation of protocol amendment #4 for the remaining participants in the study all tumor assessments in the post-treatment follow-up period will be optional and will be left at the discretion of the investigator

1.2 Study objectives and endpoints

Objectives and related endpoints are described in [Table 1-1](#) below.

Table 1-1 Objectives and related endpoints

Objective(s)	Endpoint(s)
Primary objective(s)	Endpoint(s) for primary objective(s)

To assess the antitumor activity of the three treatment arms LAG525 + spartalizumab, LAG525 + spartalizumab + carboplatin and LAG525 + carboplatin, in subjects with advanced TNBC in first or second line of therapy, as measured by the objective response rate (ORR) per investigator's assessment according to RECIST v1.1.	
Overall response rate (ORR) per RECIST v1.1 per investigators' assessment
Secondary objective(s)	Endpoint(s) for secondary objective(s)

To assess the efficacy of the three treatment arms with respect to Duration of response (DOR), Time to response (TTR), Progression Free Survival (PFS) and Clinical benefit rate (CBR) per investigator's assessment according to RECIST v1.1To assess Overall Survival for each treatment armTo characterize the safety profile of each treatment armTo characterize the pharmacokinetics (PK) of LAG525, spartalizumab, and carboplatin in the three investigated combinationsTo assess immunogenicity of LAG525 and spartalizumab in the three investigated combinations	
Duration of response (DOR), Time to response (TTR), PFS and Clinical benefit rate (CBR) per investigators' assessment.Overall Survival (OS)Adverse events (AEs), serious AEs (SAEs), changes in hematology and chemistry values, vital signs, weight, ECOG performance status, electrocardiograms (ECGs), dose interruptions, reductions and dose intensity.Pharmacokinetic parameters (e.g., Ctrough, Cmax, AUC)Antidrug antibodies (ADA) prevalence at baseline and ADA incidence on treatment

2 Statistical methods

2.1 Data analysis general information

The primary analysis and final analysis will be performed by Novartis and/or a designated CRO. SAS version 9.3 or later and R version 3.2.3 or later software will be used to perform all data analyses and to generate tables, figures and listings.

Data included in the analysis

The analysis cut-off date for the primary analysis of study data was established after all randomized subjects have been followed for efficacy (tumor assessments) for at least 24 weeks or discontinued tumor assessments for any reason prior to 24 weeks. All statistical analyses will be performed using all data collected in the database up to the data cut-off date. All data with an assessment date or event start date (e.g. vital sign assessment date or start date of an adverse event) prior to or on the cut-off date will be included in the analysis. Any data collected beyond the cut-off date will not be included in the analysis and will not be used for any derivations.

All events with start date before or on the cut-off date and end date after the cut-off date will be reported as ‘ongoing’. The same rule will be applied to events starting before or on the cut-off date and not having documented end date. This approach applies, in particular, to adverse event and concomitant medication reports. For these events, the end date will not be imputed and therefore will not appear in the listings.

The analysis cut-off date for the final analysis of study data will be established at the end of the study, when all subjects have died or discontinued from the study, or another clinical study became available that can continue to provide study treatment in this subject population and all subjects ongoing are eligible to be transferred to that clinical study.

General analysis conventions

Pooling of centers: Unless specified otherwise, data from all study centers will be pooled for the analysis. Due to expected small number of subjects enrolled at centers, no center effect will be assessed.

Qualitative data (e.g., gender, race, etc.) will be summarized by means of contingency tables by treatment arm; a missing category will be included as applicable. Percentages will be calculated using the number of subjects in the relevant population or subgroup as the denominator.

Quantitative data (e.g., age, body weight, etc.) will be summarized by appropriate descriptive statistics (i.e. mean, standard deviation, median, minimum, and maximum) by treatment arm.

